Specific Aims

In 2013, the United States Preventive Task Force (USPSTF) recommended use of annual low dose CT scans (LDCT) to screen high-risk individuals for lung cancer. This recommendation was based on evidence that detecting and treating early-stage lung cancer would greatly lower the risk of dying from this disease. Unfortunately, lung cancer screening rates in the United States are very low— just 3.3% in 2010 and 3.9% in 2015 (1). **Not yet known** is how to effectively promote and increase lung cancer screening while supporting patients and physicians in making this high stakes decision. There is a critical need to develop and implement effective strategies to engage high risk patients, those who have a substantial history of smoking, in a coordinated program of lung cancer screening which includes shared-decision making.

The **long term goal** of this work is to decrease lung cancer mortality through primary care interventions. Such interventions should leverage the patient-physician relationship and support patients to make informed decisions about lung cancer screening that is aligned with current medical evidence and emphasizes patient values and preferences. In 2017, our research team took an initial step to towards achieving this goal by assessing the feasibility of implementing an informed decision making intervention in a single primary care practice among 54 patients who were eligible for lung cancer screening. The intervention centered the Decision Counseling Program ® (DCP)(2) an online software application that focuses on patient education and preference clarification related to lung cancer screening delivered over the phone by a trained nurse educator. DCP results were given to patients and providers. Use of the DCP intervention was feasible, helped primary care patients clarify their preference related to screening, and participants were likely to undergo LDCT screening. We now propose to **modify and expand the intervention**. We will recruit 100 eligible, current smokers from real world primary care practices to participate in a pilot study, outlined in **Figure 1** comparing to usual care by propensity scoring.

[figure not shown]
Aim 1 Compare low dose CT scan completion in the DCP cohort of current smokers versus usual care, propensity-matched controls at 60 days.

Aim 2 Compare the characteristics of the patients not recruited in the study to the characteristics of those who accepted to enroll

Aim 3 Test the feasibility of intensive smoking cessation as part of the DCP.

Lung cancer is the leading cancer killer in the United States and effective lung cancer screening could have significant public health

impact. This work advances the mission of ACCEL advancing translational science by developing best practices to implement evidence-based prevention in real world clinical practice. This work will advance the implementation of clinical guidelines for lung cancer screening and shared decision making as well advance understanding of health disparities associated with lung cancer screening. Effective implementation of a shared decision making process in primary care would serve as a model for future expansion to other diseases and decisions.

Significance

[figure not shown]
Lung cancer is the leading cancer killer in the United States. Each year, more people die of lung cancer than of colon, breast, and prostate cancers combined. **Lung cancer screening** or low dose CT scan (LDCT) can find early lung cancer in people at high risk and significantly lower their risk of dying from this disease. The National Lung Screening Trial (NLST) was a randomized trial of low dose CT scan (LDCT) versus chest x-ray in individuals at high risk for lung cancer (3). The NLST demonstrated a 20% reduction in mortality. In 2013, based on the NLST, the United States Preventive Task Force (USPSTF) recommended use of LDCT to screen for lung cancer in high risk individuals; high risk individuals are defined as people between the ages of 55 and 80 years old, with a 30 pack year history of smoking, who either currently smoke or quit less than 15 years ago (level B recommendation) (4). In response to the USPSTF recommendation, the Center for Medicare and Medicaid Services (CMS) announced that lung cancer screening (LCS) will be included as a covered benefit. However, CMS requires that "a beneficiary must receive a written order for LDCT lung cancer screening during a lung cancer screening counseling and shared decision making visit." This CMS requirement for shared decision making is a first and highlights that lung cancer screening is a high stakes decision. Lung cancer screening is a high stakes decision because the potential mortality benefit for LCS is very high but rests on a single randomized controlled trial. This benefit is counterbalanced by the risks of false positives and incidental findings which may lead to invasive procedures e.g. bronchoscopy and even thoracic surgery. All screening tests are associated with the risk of a false alarms, unnecessary treatment and incidental findings. This CMS requirement for shared decision making is likely to become a common requirement and raises the question of how to best implement shared decision making in real world clinical practice. More importantly, patients prefer shared decision making and the active role it brings to their health care and patients who have share in decision making have better health outcomes and satisfaction with care (5). Our intervention is based on the Preventive Health Model in **Figure 2**. (6, 7).

Innovation

Best practices for implementing high quality informed or shared decision making in primary care are not developed. High quality, shared decision making in medical care should be based on sound clinical evidence, patient education and should include the values, preferences and beliefs of the patient. However, real world clinical practice does not routinely support high quality shared decision making. Most medical care decisions are prompted during a visit with a health care provider and often such visits are brief and focused on acute care (e.g. a "cold") or episodic care (e.g. ongoing management of chronic diabetes). So, patients are usually asked, with little or no preparation, to consider and make high stakes medical decisions such as lung cancer screening. Innovative ways to prepare and support patients and their physicians in complex decision making are needed. Effective implementation of such innovations would be non-disruptive to other ongoing care needs and would leverage the relationship between the patient and their physician. This intervention is **patient-centered** and **proactive** moving outside of the physician-patient visit to reach patients who may be unaware of their own eligibility. Recognizing that physician recommendation is typically one of the strongest predictors of cancer screening, this intervention builds on the patient-physician relationship and allows other team members to practice at the top of their license, a potential for cost-savings. Most importantly, this intervention would prepare the patient to make the most of face to face encounter with their physician and to make the best personal decision. Lung cancer screening represents a teachable moment for a group of heavy smokers. By pairing intense, tailored smoking cessation efforts to lung cancer screening, the benefit of lung cancer screening will be amplified by improving multiple health outcomes associated with smoking cessation.

Approach

Preliminary Studies The DCP ® intervention was implemented in one family medicine practice. Using electronic medical record (EMR) data, we identified a list of over 900 potential enrollees (both current and former smokers age

55-74). There were 297 individuals who were reachable and 54 of these were eligible for LCS according to the USPSTF criteria. We were able to contact a higher proportion of current smokers (47%) than former smokers (30%). Eligibility was higher in current smokers (28%) versus former smokers (11%). Also, of the 54 total eligible, 28 enrolled. Despite these small numbers, we were able to show the DCP participation was associated with LDCT completion at 90 days ($p=0.03$).

Study Design We propose a 1 year project including a **6 month intervention** period. This study will be a cohort with comparison to usual care in other practices in the same health system using propensity-matching methodology. **Study population/eligibility** Inclusion/exclusion criteria will be based on the USPSTF and CMS lung cancer screening guidelines: age 55- 80, with a 30 pack year smoking history, no symptoms consistent with cancer, and no CT scan of the lungs within the last year. Physicians will be given the chance to eliminate participants based on limited life expectancy or prohibitive comorbid conditions. Case finding in our prior work was difficult and recruiting active smokers has a higher yield. Prior work indicated that this pool yielded a higher proportion of truly eligible, reachable individuals. Plus, we want to test the feasibility of a more intense smoking cessation intervention. To address recruitment barriers, we will work with practices and PCPs to promote as a study “conducted with the PCP,” including the physician name or practice name when possible on recruitment materials e.g. written letters and email cosigned by their PCP. To address case finding barriers, we will allow patients to easily opt out of future contact via mail, email or phone. We will work with our advisory panel to explore other methods to enhance recruitment and case-finding such as using the secure EMR portal to screen for LCS eligibility and/or updating smoking history. Finally, we have added \$50 patient incentives per patient for participation.

Intervention The DCP is an online software application that supports an interactive session that focuses on patient education and preference clarification. Patients will be contacted by phone or other methods to provide information about the study, be invited to participate, consented, and then scheduled for decision counseling. Neither the DCP tool nor this process is directive; the DCP session does not push the patient to screen but, rather, clarifies the patient's current preference (screen or not) and identifies key reasons for that preference. In the session, the decision counselor and patient will review the options, (to screen or not to screen for lung cancer) using publicly available patient education materials (Appendices 1 & 2) (8, 9). Then, the decision counselor will guide the patient through 5 steps: 1) identify factors most likely to influence the decision to screen 2) assign importance (decision weight) to the factors 3) compare the relative weight of the most important factors 4) generate a decision score, and 5) generate a personal summary form which can be made available in the EMR for physician review with the patient. Next steps will be tailored to each practice, and can include referral to PCP for further discussion and/or referral to the Lung Health Screening Program (LHSP). The decision counselor will be trained as a smoking cessation coach and as a “mini-expert” in system and community resources for smoking cessation.

Data Acquisition Following approval by the CCHS Institutional Review board, lists of potentially eligible individuals from participating and non-participating practices will be obtained from EMR data. These lists will be automatically entered into a REDCap® for CONSORT tracking. Lists will be organized according to PCP whom will be given 7 working days to review lists and eliminate any patient they feel would not be appropriate for this study. Remaining potentially eligible patients will receive a letter, cosigned by their personal physician which introduces the study and offers the opportunity to easily opt out of further contact. After an opt-out period of 7 working days, patients will be contacted, screened for eligibility and invited to participate. After formal consent, we will collect demographics, socioeconomic variables and smoking history. Baseline data will be collected regarding knowledge, preference and decisional conflict related to lung cancer screening. Standard patient education materials will be sent to patients. The DCP session will be conducted within 30 days of enrollment. A follow up telephone call will occur within 30 days of DCP completion, and will include items to assess patient perception of the process, knowledge about lung cancer screening and decisional conflict (Appendix 3) related to lung cancer screening (10). At 60 days after the decision counseling session, patient charts/electronic medical record data will be audited for the primary outcome, LDCT scan report. Prior work showed the average time from DCP to LDCT was ≤ 60 days. Intermediate (process) outcomes in EMR include lung cancer screening discussion, referral/order for LDCT, or referral to the CCHS LHSP. Eligible patients in the usual care group (in the non-participating clinics) will be identified electronically as stated above and LDCT screening assessed in a 60 day study period from their most recent office visit. Information available in EMR for all patients including controls and individuals who are “unreachable” comprises gender, age, race, ethnicity, insurance status, marital status, smoking status, comorbidities, such as COPD, Heart disease, diabetes, hypertension and zip code (surrogate for socioeconomic status). Information collected from individuals who are reached but ineligible will include all of the above plus smoking status, pack years, and reason for ineligibility. Information collected from individuals who decline participation will include all of the above plus reason for declining participation.

Statistical analysis

Aim 1 Compare low dose CT scan completion in the DCP cohort of current smokers versus usual care propensity-matched controls at 60 days. *Hypothesis: Participation in the DCP will be associated increased participation in LDCT, compared with both eligible enrollees who do not participate and with eligible patients in usual care practices.* Demographic and clinical variables of the intervention and control groups will be compared using T-Test, Wilcoxon-Rank sum test and chi-squares. We will conduct a 1-to-1 propensity score matching to compare the proportion of patients who screen between the groups. We will use a logistic regression model to build propensity scores to match patients in the intervention and control groups. We will model the probability of being in the intervention group using all the patients level variables extracted from the medical records as listed above. Whether they are in a participating practice or not will not be included in the model as an independent variable. The nearest neighborhood method without replacement will be used for matching. We will set the caliper width according to the standard deviation for the propensity score. Each control will be assigned a probability score and matched with a patient in the intervention group. In a second step, we will compare the characteristics of the patients and chosen controls to verify that they are very similar. We will use a simple chi-square to compare the percentage of patients in the control and intervention groups who complete the LDCT scan within 60 days.

Power calculation based on primary outcome: According to our preliminary study, 45% of those who complete the DCP decided to screen for lung cancer whereas the know rate of screening among patients in usual care is 15%, which makes a difference of 30%. A sample size of 40 patients in each group will achieve 85% power to detect a difference between the group proportions of 30%. The proportion in the intervention group is assumed to be 15% under the null hypothesis and 45% under the alternative hypothesis. To detect a difference of 20%, we will need a sample size of 60 patients in each group to achieve a power of 80%. We expect that 2000 patients will be identified as potentially eligible for the study in the EMR and 1000 will be reachable. Of those 300 (30%) will be confirmed eligible during the phone call and 150 (50%) will accept to participate in the DCP. We will therefore have ample power to detect a difference as small as 20% between our 2 groups.

Aim 2 Compare the characteristics of the patients not recruited in the study to the characteristics of those who accepted to enroll. *Hypothesis: Patients recruited to the study versus those who are not will be different demographically and geographically.* We will use descriptive statistics to examine the characteristics of the patients of the intervention practices who were eligible but could not be reached and of the patients who were reached but refused to be in the study. We will also compare the characteristics of these patients to those of the patients who enrolled in the study. We will use logistic regression models to determine which independent characteristics are associated with agreeing to be in the study.

Aim 3 Test the feasibility of intensive smoking cessation as part of the DCP. *This aim is hypothesis generating.* At 30 days, we will ask patients about participation in smoking cessation, quit attempts and for general comments on their needs and satisfaction with our smoking cessation efforts. We will explore trends associated with these intermediate outcomes related to cessation including engaging in cessation and quit attempts. We will illicit qualitative information from participants about how to make this part of the program useful and patient-centered.

Community Engagement Our team has established relationships with clinical and administrative leadership as would be necessary to conduct this work in a large health system. In addition, we have engaged local community outreach leaders with special knowledge and emphasis on smoking cessation. [name] is a frequent speaker for physician educational events locally, regionally and nationally. In the first two months of the project, we will convene an advisory team of patients, physicians and administrative leaders to guide and champion this work. The advisory team will provide expertise on improving lung cancer screening generally and provide specific advice regarding: practice selection, data acquisition and exchange, improving recruitment methods, adding smoking cessation and planning for sustainability beyond the pilot funding period.

Sustainability This work would lay the groundwork for an R01 level randomized controlled trial. The Agency for Healthcare Research and Quality (AHRQ) has issued a Special Emphasis Notice (SEN) to inform the research community that AHRQ intends to support research on models of shared decision making (SDM) that are tailored to the needs of low income and racial and ethnic minority patients (11). The Patient Centered Outcomes Research Institute (PCORI) has a strong focus on comparative effectiveness research which helps patients to make informed or shared decisions (12). The use of non-physician team members to extend care beyond the visit and to provide proactive care is likely to be cost-effective in improving population health and is aligned with the strategic vision of CCHS.

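### The plan recruits 100 but bases its power claim on 150, makes no allowance for non-completion or matching loss, and gives 60 per group where 73 to 89 are needed

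*Combined protocol and SAP*

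**What the plan says.** The Specific Aims set the size of the study: "We will recruit 100 eligible, current smokers".

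The power calculation paragraph of the Statistical analysis section does not mention 100. It gives two requirements: 40 per group for 85% power at 45% v 15%, and 60 per group for 80% power at a 20-point difference. It then projects recruitment: "We expect that 2000 patients will be identified as potentially eligible for the study in the EMR and 1000 will be reachable", and "Of those 300 (30%) will be confirmed eligible during the phone call and 150 (50%) will accept to participate in the DCP". The next sentence draws the conclusion: "We will therefore have ample power to detect a difference as small as 20% between our 2 groups".

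Three other statements bear on the number analysed:

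- Under Aim 1, matching is 1-to-1, nearest neighbour, without replacement and within a caliper. The two groups are then compared by a chi-square test.
- The Aim 1 hypothesis foresees eligible enrollees who do not take part. Data Acquisition places the session up to 30 days after enrolment.
- The 45% rate in the power paragraph applies to patients who completed the DCP.

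The plan states no alpha, sidedness, completion rate, match rate or caliper multiple.

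**The concern.** The power conclusion follows directly from the expected 150, so it does not describe a study that stops at the 100 named in the Specific Aims. A reader cannot tell which number the power statement belongs to.

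Neither number is the one that enters the test. An enrollee without a session falls outside the group to which the 45% applies. A DCP patient with no control inside the caliper is dropped from the comparison. The plan provides for both routes of loss and quantifies neither.

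The yardstick for adequate power, 60 per group, does not agree with the plan's own 40-per-group calculation. If 60 is too low, the distance from the target to the requirement is smaller than it appears.

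At stake is how an Aim 1 result can be read. If the difference is near 20 points and the test is not significant, the reader needs to know what power and precision the matched sample had. The plan also intends this pilot to prepare a larger randomised trial.

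**Working it through.** **Inputs.** Rates of 45% and 15%, 40 and 60 per group, 85% and 80% power, and 150 expected are from the power paragraph. The target of 100 is from the Specific Aims. The 1:1 ratio and the chi-square test are from Aim 1. Alpha of 5% is assumed. The plan does not say which rates make up the 20-point difference, so two readings are used: 35% v 15% (usual care as stated) and 45% v 25% (DCP rate as stated).

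**Formula.** With n per group, d = p1 − p2 and p̄ = (p1 + p2)/2:

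power = Φ{ [d√n − 1.96·√(2p̄(1 − p̄))] / √(p1(1 − p1) + p2(1 − p2)) }

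**Step 1: reproduce the plan's first figure.** For 45% v 15% and n = 40: (1.897 − 1.270)/0.612 = 1.024, so power is 84.7%. This matches the stated 85%. A one-sided 5% test would give 91.3%, so two-sided 5% is the convention that fits.

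**Step 2: the plan's second figure under the same convention, n = 60.**

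- 35% v 15%: (1.549 − 1.200)/0.596 = 0.586, power 72.1%.
- 45% v 25%: (1.549 − 1.322)/0.659 = 0.344, power 63.5%.

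Solving for 80% power, n = [(1.96·√(2p̄(1 − p̄)) + 0.842·√(p1(1 − p1) + p2(1 − p2)))/d]². This gives 72.4, so 73 per group, for 35% v 15%, and 88.1, so 89 per group, for 45% v 25%. A one-sided test brings 60 per group to 81.8% for 35% v 15%, but that convention fails Step 1.

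**Step 3: the recruitment projection.** 2000 × 0.50 = 1000; 1000 × 0.30 = 300; 300 × 0.50 = 150. The arithmetic is correct.

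**Step 4: power at 100 and at 150 matched pairs, no losses.**

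| Scenario | 100 pairs | 150 pairs |
|---|---|---|
| 35% v 15% | 91.0% | 98.2% |
| 45% v 25% | 84.8% | 95.6% |
| 45% v 15% | over 99% | over 99% |

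The 95% confidence interval half-width is 1.96·√[(p1(1 − p1) + p2(1 − p2))/n]. For 35% v 15% it is 1.96·√(0.355/100) = 11.7 points at 100 pairs and 1.96·√(0.355/150) = 9.5 points at 150.

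**Step 5: combined loss to non-completion and matching.** The documents give no rates, so a range is shown.

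| Start | Loss | Pairs | 35% v 15% | 45% v 25% | 45% v 15% |
|---|---|---|---|---|---|
| 100 | 10% | 90 | 87.9% | 80.8% | 99.5% |
| 100 | 20% | 80 | 83.8% | 76.0% | 98.9% |
| 100 | 30% | 70 | 78.6% | 70.3% | 97.9% |
| 100 | 40% | 60 | 72.1% | 63.5% | 95.7% |
| 150 | 20% | 120 | 95.2% | 90.6% | over 99% |
| 150 | 40% | 90 | 87.9% | 80.8% | 99.5% |

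The loss at which power reaches 80% is 1 − 73/100 = 27% from 100 and 1 − 73/150 = 51% from 150 for 35% v 15%. For 45% v 25% it is 1 − 89/100 = 11% and 1 − 89/150 = 41%.

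**The case against.** The strongest reply is that the two figures are different quantities. One hundred is a recruitment target. One hundred and fifty is an expected yield, and an expected yield above the target is no contradiction. This stands as a possible reading, and a figure missing from the available copy might bear on it. But the text does not say so, and on that reading the power conclusion should have been drawn from 100.

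A second reply is that 100 exceeds both the plan's 60 and the corrected 73 and 89, so the conclusion survives. Before losses it does. The main 45% v 15% scenario stays above 95% power even at 40% loss from 100.

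Two stronger readings are tempting, and neither is supported:

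- A reader might infer that the study is underpowered at 100. That requires loss rates that appear nowhere in the documents. One assumed pair, such as 20% without a session and 10% unmatched, gives 100 × 0.8 × 0.9 = 72 pairs and about 80% power for 35% v 15%, but this only illustrates the calculation.
- A reader might infer that 150 is inflated, because the pilot reached 47% of current smokers and found 28% eligible, against the plan's 50% and 30%. Adding the pilot's enrolment of 28 of 54 gives 2000 × 0.47 × 0.28 × 28/54 = 136. But the 28 of 54 covers current and former smokers together, and at 51.9% it lies above the plan's 50%. The study also adds incentives and letters cosigned by the physician. The 136 is not a current-smoker yield, and the projection need not be restated.

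**Conclusion.** The point holds as an inconsistency between sections, an omission and one wrong figure. The target and the number behind the power claim differ and are not reconciled in the available copy. The number that will be analysed is never estimated. The 60 per group overstates power by about 8 points (72.1% against 80%) for 35% v 15% and about 16 points (63.5% against 80%) for 45% v 25%.

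The consequence is limited. The choice between 100 and 150 does not by itself take power below 80% in any scenario examined. It changes the margin for loss at a 20-point difference: 27% against 51% in one reading, 11% against 41% in the other.

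These results assume a two-sided 5% test with pooled variance, which is inferred from the plan's 40-per-group figure, and equal groups compared as independent samples, as the plan's chi-square test does. Actual losses are unknown.

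**What to change.** - Give one recruitment target in the Specific Aims and in the power paragraph. If 100 is the target, label 150 as the available pool.
- State alpha and sidedness.
- State the two rates behind the 20-point difference, and replace 60 per group with 73 (35% v 15%) or 89 (45% v 25%), if two-sided 5% is confirmed.
- State the expected completion and match rates, with a range. Replace the claim of ample power with power and confidence interval width at the resulting number of matched pairs.

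The cost is a text edit and a slightly less favourable stated power. No extra patients are needed.

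### Earlier LDCT screening is neither matched nor checked for balance, so patients last scanned more than 12 months ago could bias Aim 1 by an estimated 1 to 5 points

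*Combined protocol and SAP*

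**What the plan says.** Eligibility (Approach, Study population/eligibility) rests on age, pack-years, symptoms and recent imaging. The imaging part reads "no symptoms consistent with cancer, and no CT scan of the lungs within the last year". Physicians may also remove patients, on grounds unrelated to earlier screening: "Physicians will be given the chance to eliminate participants based on limited life expectancy or prohibitive comorbid conditions". Specific Aims describes the guideline behind the study as one that "recommended use of annual low dose CT scans (LDCT) to screen high-risk individuals for lung cancer".

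Under Data Acquisition, 60 days after the counseling session, "patient charts/electronic medical record data will be audited for the primary outcome, LDCT scan report". Usual-care patients "will be identified electronically as stated above and LDCT screening assessed in a 60 day study period from their most recent office visit". The EMR information available for everyone, controls included, "comprises gender, age, race, ethnicity, insurance status, marital status, smoking status, comorbidities, such as COPD, Heart disease, diabetes, hypertension and zip code".

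Under Statistical analysis, Aim 1, the propensity model is built "using all the patients level variables extracted from the medical records as listed above". Matched patients are then compared on their characteristics, and 60-day completion is compared by chi-square. No section separates first from repeat scans or plans an analysis by earlier screening.

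**The concern.** The plan treats LDCT as an annual test but looks back only 12 months. A patient leaves the exclusion window just as the next scan falls due. Someone who has had one screening LDCT is plausibly more likely to have another within 60 days than someone who has never had one, whatever the counseling does.

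That would matter little if such patients were equally common in both groups, but the design gives no assurance of this. DCP patients volunteer for a lung screening study, and the plan expects about half of confirmed eligible patients to accept. Controls are picked electronically from other practices and do not volunteer. Earlier screeners may be readier to enroll, or some practices may screen more than others, so the imbalance could run either way. Because prior LDCT is not extracted, the balance table would look the same whether or not the groups differed on it.

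**Working it through.** **Inputs from the documents.** Usual-care screening 15% and DCP screening 45% (Power calculation); planning differences of 30 and 20 points (same place); recruitment target 100 and national screening rates of 3.3% (2010) and 3.9% (2015) (Specific Aims).

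**Assumptions, because the documents are silent.**
- f_D and f_C are the shares of the DCP and control groups whose last screening LDCT was more than 12 months ago.
- r, completion within 60 days in those patients, is 40% to 60%.
- Never-screened patients complete at 15% without the DCP. The plan gives 15% for usual care as a whole and names no time window, so this too is an assumption.
- Two-sided alpha is 0.05.

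**Step 1. The plan's own figure.** For 45% v 15% with 40 per group and a pooled chi-square, the mean proportion is 0.30.
- SE under the null = √(2 × 0.30 × 0.70 / 40) = 0.1025.
- SE under the alternative = √((0.45 × 0.55 + 0.15 × 0.85) / 40) = 0.0968.
- Power = Φ((0.30 − 1.96 × 0.1025) / 0.0968) = 84.7%.

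This agrees with the stated 85%, so 15% and 45% are a sound base for what follows.

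**Step 2. False difference if the DCP has no effect.** Completion in a group is f × r + (1 − f) × 0.15. Subtracting one group from the other gives

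false difference = (f_D − f_C) × (r − 0.15).

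| Imbalance | r = 40% | r = 60% |
|---|---|---|
| 3.9 points (3.9% v none) | 0.039 × 0.25 = 1.0 point | 0.039 × 0.45 = 1.8 points |
| 5 points | 0.05 × 0.25 = 1.25 points | 0.05 × 0.45 = 2.25 points |
| 10 points | 0.10 × 0.25 = 2.5 points | 0.10 × 0.45 = 4.5 points |

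The sign reverses if controls hold more earlier screeners. The first row takes the 2015 national rate as the whole share in one group and zero in the other.

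**Step 3. Size against the planning differences.** A bias of 1.25-2.25 points is 6-11% of a 20-point difference and 4-8% of a 30-point difference. A bias of 2.5-4.5 points is 12.5-22.5% and 8-15%.

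**Step 4. Effect on the test.** This uses the Step 1 formula with both tails, 100 per group and no DCP effect.
- Shares of 10% v 5% give completion of 17.5% v 16.25% (r = 40%) or 19.5% v 17.25% (r = 60%). The false-positive rate rises from 5% to about 5.6% or 6.9%.
- Shares of 15% v 5% give 18.75% v 16.25% or 21.75% v 17.25%. The rate rises to about 7.5% or 12.6%.

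**Step 5. Equal shares.** If both groups hold the same share f and the DCP does not change repeat scanning, a true effect among never-screened patients is multiplied by (1 − f). A 20-point effect becomes 20 × 0.95 = 19 points at f = 5%, or 20 × 0.90 = 18 points at f = 10%. This is dilution, not confounding.

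**The case against.** The case against giving this much weight has four parts.

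- **Few patients may be affected.** Anyone scanned in the past 12 months is already out, which removes most people who keep to an annual schedule. Only those just due or overdue remain. With national screening at 3.3-3.9%, the share could be small. This stands and is why the lower end of the range is more likely. The local share is unknown, however, and the plan itself assumes 15% in usual care.
- **The 40-60% repeat rate has no source in the documents.** It may be too high for overdue patients, who have already missed a date. This also stands, and a lower rate shrinks the bias in proportion to (r − 15%).
- **Aim 1 asks about LDCT completion, not first uptake.** Eligibility follows the USPSTF and CMS guidelines, and the DCP clarifies current preference. A reader might infer that any repeat scan is a wrong count of the outcome. The documents do not support that: a repeat scan is a legitimate outcome under the stated aim, and the difficulty arises only if earlier screeners are unevenly spread.
- **Imbalance is conjecture.** No passage shows it. That is true, but as planned nobody could find out, because the variable is not extracted.

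**Conclusion.** The point holds as an omitted matching variable. Earlier LDCT screening is a plausible strong predictor of the outcome. It is neither an exclusion beyond 12 months nor a covariate, and the balance check cannot reveal it. Under the stated assumptions the false difference is about 1.3-2.3 points for a 5-point imbalance and 2.5-4.5 points for a 10-point imbalance, direction unknown. That is modest beside differences of 20-30 points and would not by itself produce or erase an effect of that size.

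Two stronger readings should be resisted. A reader might infer that patients in annual screening enter freely and that recent imaging is the only bar to entry. In fact age, pack-years, symptoms and physician review also exclude, and so does any lung CT within the year. A reader might also extend the table to a 20-point imbalance, which gives 5-9 points. That needs at least 20% earlier screeners in one group, above both the 3.9% national rate and the plan's 15% for usual care, and nothing in the documents supports it.

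The stated sample sizes and power are unaffected. This is an inexpensive improvement to make before matching, not a flaw that invalidates the comparison.

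**What to change.** 1. Extract any prior screening LDCT (yes/no, with date) for both groups with the same EMR query. Count only scans before each patient's 60-day window opens, so that an outcome scan is never classed as prior.
2. Match exactly on the yes/no field, or add it to the propensity model. Show it in the balance table either way.
3. Report Aim 1 in patients with no prior LDCT on record as a sensitivity analysis, and give the number of first and repeat scans in each group.

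Leave eligibility as it is. Excluding every earlier screener would change the guideline-based target population, which is a separate trade-off and is not needed to deal with the confounding.

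The cost is one field from imaging records that the plan already needs for the one-year CT criterion and the outcome. Slightly fewer controls will fall within the caliper. LDCTs done outside the health system will be missed in both groups, so some misclassification will remain and should be stated as a limitation.
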